# Study design and methods

- A. The primary aim of this study is to compare the reliability of self-collected specimens versus physician-collected specimens in detecting high-risk HPV. This clinical trial is being carried out at multiple centers in Taiwan with laboratory technicians being blind of the sample sources.
- B. The trial aims to assess how well regular women can collect specimens using self-collection kits without professional assistance
- C. To ensure effective specimen collection by ordinary women, visual aids and pre-recorded audio and video materials will be provided for self-learning. Participants will then answer a questionnaire to verify the clarity of the instructional materials. Before HPV testing, the laboratory will verify the specimen's integrity by testing for beta-globin DNA.
- D. Subject inclusion procedures:
- 1. Eligible women who agree to participate will sign a consent form after receiving an explanation from the doctor.
- 2. Once the predetermined number of participants is reached, no further subjects will be enrolled, and the test results will be revealed and analyzed statistically.
- E. Sample collection procedure:
- 1. After obtaining consent, the study nurse will provide a coded self-sampling swab to each subject for self-collection. Cervical cell collection by the physician will follow routine procedures in the outpatient clinic. The self-sampling swabs are randomly coded to ensure blinding for laboratory test operators.
- 2. Physician examination:
- (1) Doctors use a cytological brush to collect cervical cells in accordance with medical routine during the outpatient clinic.
- (2) The specimens collected for examination will be kept by nurses and sent to the National Tsing Hua University laboratory.
- (3) Vaginal lavage or intravaginal medication should be avoided before specimen collection. Additional tests like smear examination or colposcopy may be conducted if necessary.
- 3. Self-sampling:
- (1) Subjects will receive a "HygeiaTouch Self-sampling Kit for Women" containing a sterile self-sampling swab and sample collection tube. They must read the instruction manual, watch an instructional video, and confirm their understanding by answering questions.
- (2) After self-sampling, subjects will place the swab in the collection tube and hand it to the study nurse.

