# **Subject inclusion conditions**

Subjects must meet the following three conditions:

- A. aged 21 years and above (inclusive) and below 65 years old (inclusive) who have not undergone total hysterectomy and uterine / cervical radiation therapy
- B. Understand the trial content and sign the subject consent form
- C. Those who meet one of the following 5 conditions:
- 1. Those with no abnormal smears or history of cervical lesions
- 2. Those who have had mild smear or pathological tissue abnormalities within 3-12 months and need to undergo cervical smear follow-up

Mild smear abnormalities include atypical squamous cells of undetermined significance, cervical intraepithelial neoplasia grade 1, or atypical glandular cells.

3. Have had moderate to severe smear or pathological tissue abnormalities or cervical cancer, have undergone cone surgery, and are currently being followed

Including smear is atypical squamous cells favor high-grade squamous intraepithelial lesion atypical squamous cells favor high-grade squamous intraepithelial lesion, the cytopathology cannot exclude high-grade squamous intraepithelial lesion dysplasia cannot exclude high-grade squamous intraepithelial lesion, smear or histopathology is Cervical intraepithelial neoplasia grade 2, Cervical intraepithelial neoplasia grade 3, Cervical carcinoma in situ, Cervical squamous cell carcinoma, or atypical glandular cells favor neoplasm, cervical adenocarcinoma in situ, or cervical adenocarcinoma.

4. Those who have mild smear or pathological tissue abnormalities within 3 months and have not yet been treated

Mild smear abnormalities include atypical squamous cells of undetermined significance, cervical intraepithelial neoplasia grade 1, or atypical glandular cells.

5. Those who have found moderate to severe smear or pathological tissue abnormalities or cervical cancer within 3 months and have not yet received treatment

Including smear shows atypical squamous cells favor high- grade squamous intraepithelial lesion, smear test or histopathology is Cervical intraepithelial neoplasia grade 2, Cervical intraepithelial neoplasia grade 3, Cervical carcinoma in situ, Cervical squamous cell carcinoma, or atypical glandular cells favor neoplasm, cervical adenocarcinoma in situ, or cervical adenocarcinoma.

The above groupings are also the basis for stratification of the statistical analysis of this trial.

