## **Inclusion criterias**

**Participants must meet the following three conditions:**

- A. Women over 21 years old (inclusive) and under 65 years old (inclusive), who have never received total hysterectomy and never received radiation therapy for the uterus / cervix
- B. Understand the content of the experiment and sign the subject's consent form
- C. meet one of the following 5 conditions :

1. No history of abnormal smear or cervical lesions
2. There have been mild smears or pathological abnormalities within 3-12 months, and those who need to receive Pap smear follow-up

Mild smear abnormalities include atypical squamous cell of undetermined significance, first-degree cervical intraepithelial neoplasia grade 1, or atypical glandular cell.

3. Those who have had moderate to severe smear or pathological abnormalities or cervical cancer, have undergone conical surgery, and are currently receiving follow-up

Including atypical squamous cells favor high-grade squamous intraepithelial lesion in smear, cytopathic lesion cannot exclude high-grade squamous intraepithelial lesion, smear or histopathology is cervical intraepithelial neoplasia of the second degree lasia grade 2, cervical intraepithelial neoplasia grade 3, cervical carcinoma in situ, squamous cell carcinoma of the cervix, or atypical glandular cells favor neoplasm, adenocarcinoma in situ of the cervix, or Cervical adenocarcinoma patients.

4. Mild smear or pathological tissue abnormalities within 3 months without treatment

Mild smear abnormalities include atypical squamous cell of undetermined significance, first-degree cervical intraepithelial neoplasia grade 1, or atypical glandular cell.

5. Moderate or severe abnormalities in smear or pathological tissue or cervical cancer found within 3 months, and those who have not received treatment

Including atypical squamous cells favor high-grade squamous intraepithelial lesion in smear, cytopathic lesion cannot exclude high-grade squamous intraepithelial lesion, smear or histopathology is cervical intraepithelial neoplasia of the second degree lasia grade 2, cervical intraepithelial neoplasia grade 3, cervical carcinoma in situ, squamous cell carcinoma of the cervix, or atypical glandular cells favor neoplasm, adenocarcinoma in situ of the cervix, or Cervical adenocarcinoma patients.

stratification of the statistical analysis of this experiment.

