**All data included in the output table of the analysis**

Figure 1. Test flow chart

[figure not shown]

Table 1 Basic information of subjects

Characteristics	Total		Group 1		Group 2		Group 3		Group 4		Group 5	
	N	(N=)	N	(N=)	N	(N=)	N	(N=)	N	(N=)	N	(N=)
Age (year)												
Mean ± SD												
Median, range												
Colposcopy												
Yes												
No												
Finding												
Normal												
Punctuation												
Mosaicism												
Atypical vessels												
Condyloma accuminata												
Leukoplakia												
Invasive carcinoma suspected												
Others												
Past history of cervical histology*												
CIN1												
CIN2												
CIN3												
LSIL												
HSIL												

Squamous cell carcinoma

Adenocarcinoma

Others

None

Menopausal

No

Yes

Histological results

SM-C-

SM+

atypical

CIN1

CIN2

CIN3

SCC

AIS

Adca

clearCC

No biopsy taken

---

\*Histological diagnosis preferred

ASCUS, atypical squamous cell of undetermined significance

ASCH, atypical squamous cells favor high-grade squamous intraepithelial lesion

CIN, cervical intraepithelial neoplasia

HSIL, high-grade squamous intraepithelial lesion

LSIL, low-grade squamous intraepithelial lesion

Table 2 Smear examination results before inclusion in the trial (90 days ago)

Cytology	Total		Group 1		Group 2		Group 3		Group 4		Group 5	
	N	%	N	%	N	%	N	%	N	%	N	%
No Pap smear taken												
Within normal limit												
Reactive changes: Inflammation, repair, radiation, and others												
Atrophy with inflammation												
Atypical squamous cells (ASCUS)												
Atypical glandular cells												
Mild dysplasia (CIN1) with koilocytes												
Mild dysplasia (CIN1) without koilocytes												
Moderate dysplasia (CIN2)												
Severe dysplasia (CIN3)												
Carcinoma in situ (CIN3)												
Squamous cell carcinoma												
Adenocarcinoma												
Other malignant neoplasm												
Other												
Atypical glandular cells favor neoplasm												
Atypical squamous cells cannot exclude HSIL												
Dysplasia cannot exclude HSIL												
Endocervical adenocarcinoma in situ												

Table 3 Smear examination results when included in the trial (within 90 days)

Cytology	Total		Group 1		Group 2		Group 3		Group 4		Group 5	
	N	%	N	%	N	%	N	%	N	%	N	%
No Pap smear taken												
Within normal limit												

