aHPV 16: HPV 16 present only and/or co-infections with other types; bHPV 18: HPV 18 present only and/or co-infections with other types; cHPV 16/18: HPV16 and/or HPV18 present and/ or co-infections with other types; dHPV31, 33, 35, 39, 45, 51, 52, 56, 58, 59, 66, and 68 excluding HPV16 and HPV18 ; eHPV 6, 11, 53, 54, 61, 62, 69, 70, 72, 73, 81, 82 and 84 excluding HPV16, 31, 33, 35, 39, 45, 51, 52, 56, 58, 59, 66, and 68.

Table 8 Distribution of all measurable HPV types in medical samples and self- collected samples of each group

HPV	Total	Group 1	Group 2	Group 3	Group 4	Group 5
	( N=)	( N=)	( N=)	( N=)	( N=)	( N=)
6	Physician	Self	Physician	Self	Physician	Self
11						
16						
18						
31						
33						
35						
39						
45						
51						
52						
53						
54						
56						
58						
59						
61						
62						
66						
68						
69						
70						
72						
73						
81						
82						
84						
Negative						

Figure 2. Distribution of HPV types on physician-collected and self-collected specimens

Figure 3. Distribution of HPV types in Physician-collected and Self-collected specimens without precancerous lesions or cervical cancer (N = )

Figure 4. The distribution of HPV types on physician-collected and self-collected specimens of participants with cervical intraepithelial neoplasia grade 1

Figure 5. The distribution of HPV types on physician-collected and self-collected specimens of participants with cervical intraepithelial neoplasia grade 2 (N = )

Figure 6. The distribution of HPV types on physician-collected and self-collected specimens of participants with cervical intraepithelial neoplasia grade 3 (N = )

Table 9 Sensitivity, specificity, PPV and NPV between medically collected and self- collected HPV test results and cervical histopathology

cervical histopathology	self- collected specimen		Physician check		Relative accuracy	
	n/N	(95% CI)	n/N	(95% CI)	(95% CI)	p value
CIN1+						
Sensitivity						
Specificity						
Positive predictive value						
Negative predictive value						
CIN2+						
Sensitivity						
Specificity						
Positive predictive value						
Negative predictive value						
CIN3+						
Sensitivity						
Specificity						
Positive predictive value						
Negative predictive value						

\*No histological diagnosis is calculated as Negative

Table 10 Analysis of Satisfaction Questionnaires Included in Total Cases (N = , ITT)

satisfaction survey	very low		Low		high		very high	

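### SAP Table 9 counts every woman without histology as disease-negative, so it reports the lowest possible PPV and the highest possible NPV, with no planned check on the rule

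*SAP*

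**What the plan says.** The SAP (Secondary evaluation indicators to be analyzed, item F) plans sensitivity, specificity, PPV and NPV for the physician sample and for the self-collected sample, against the most serious pathological diagnosis. Table 9 sets these out at CIN1+, CIN2+ and CIN3+, with a Relative accuracy column. Its footnote is "No histological diagnosis is calculated as Negative", with no exception by group or threshold.

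Histology is not required of every woman. The protocol (Study design and methods, E.2(3)) says "Additional tests like smear examination or colposcopy may be conducted if necessary", and SAP Table 1 has a row "No biopsy taken".

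The entry rules allow smear alone. Group 5 is defined by "Moderate or severe abnormalities in smear or pathological tissue or cervical cancer found within 3 months" and Group 4 by "Mild smear or pathological tissue abnormalities within 3 months without treatment". The protocol's inclusion conditions make the same smear-or-tissue choice.

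Table 1 lists "Past history of cervical histology" separately from the histological results. Table 3 sets a 90-day window for smears. No such window is given for histology.

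**The concern.** A woman recruited because her smear suggests high-grade disease can be counted as a confirmed negative if no tissue was taken. An unbiopsied HPV-positive woman with disease becomes a false positive and lowers PPV. An unbiopsied HPV-negative woman with disease becomes a true negative and raises NPV. Table 9 would then print one end of a range as if it were the estimate.

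The reference standard is also not fully defined. Item F mentions smear and histopathology together, but does not say whether smear counts towards disease status. It also does not say whether a biopsy from the three months before entry counts as concurrent.

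Neither document plans bounds, imputation, a correction for partial verification or any other sensitivity analysis. The accuracy measures are a named secondary indicator, and the SAP reserves the word exploratory for analyses other than the main and secondary indicators.

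**Working it through.** **Inputs from the documents.** Recruitment shares are 10/15/20/20/35% and expected HPV positivity is 10/70/50/70/90% (SAP, Statistical considerations, item B). There are 1,200 women, with up to 10% lost to invalid samples or withdrawal (SAP, Sample size calculation).

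**Assumptions.** Losses are spread evenly over the groups, giving 1,080 valid pairs, and the same positivity applies to both samples. The share without histology and the disease rate among those women are not in the documents, so ranges are used.

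1. *The plan's own figure.* 0.10×0.10 + 0.15×0.70 + 0.20×0.50 + 0.20×0.70 + 0.35×0.90 = 0.67. The stated 67% reproduces.

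2. *Denominators.* 1,080×0.67 = 723.6 HPV-positive, leaving 356.4 HPV-negative. By group, the positives are 10.8/113.4/108/151.2/340.2 and the negatives 97.2/48.6/108/64.8/37.8.

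3. *Direction.* Let T+ and T− be the HPV-positive and HPV-negative women, D+ and D− those with histologically confirmed disease, and x and y the undiagnosed cases among the U+ and U− women without histology. Then PPV = (D+ + x)/T+ and NPV = (T− − D− − y)/T−. The footnote sets x = y = 0, which is the minimum PPV and the maximum NPV. The gaps to the opposite bounds are U+/T+ and U−/T−, whatever the disease rate.

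4. *Effect per miscoded woman.* Ten HPV-positive: 10/723.6 = 1.4 points of PPV. Ten HPV-negative: 10/356.4 = 2.8 points of NPV.

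5. *Group 5 contribution to the gap, 10-50% without histology (assumed).*
   - PPV: 340.2×0.1 = 34.0 and 340.2×0.5 = 170.1 women, or 4.7-23.5 points.
   - NPV: 37.8×0.1 = 3.8 and 37.8×0.5 = 18.9 women, or 1.1-5.3 points.
   - If half of these women have CIN2+, at the same rate in HPV-positives and HPV-negatives, PPV is understated by 2.4-11.8 points and NPV overstated by 0.5-2.7. Equal rates overstate the NPV effect if HPV predicts disease. If all the missed cases are HPV-positive (18.9-94.5 women), the PPV error is 2.6-13.1 points and NPV does not move.

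6. *Where the error sits.* Group 5 holds 340.2/723.6 = 47% of expected HPV-positives but 37.8/356.4 = 10.6% of HPV-negatives. To cause most of the error, its rate of undiagnosed disease must exceed the Groups 1-4 average by a factor of 383.4/340.2 = 1.13 for PPV, but 318.6/37.8 = 8.4 for NPV. For CIN1+, take Group 4 (216 valid, 10-50% without histology, half of them with CIN1+, all assumed). PPV moves by 216×(0.1 to 0.5)×0.5×0.7 = 7.6-37.8 women, or 1.0-5.2 points. NPV moves by 216×(0.1 to 0.5)×0.5×0.3 = 3.2-16.2 women, or 0.9-4.5 points.

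7. *Bounds over all groups.* Assume 50-90% of Groups 1-3 and 10-50% of Groups 4-5 lack histology.
   - PPV, low end: (0.5×232.2 + 0.1×491.4)/723.6 = 23 points. High end: (0.9×232.2 + 0.5×491.4)/723.6 = 63 points.
   - NPV, low end: (0.5×253.8 + 0.1×102.6)/356.4 = 38 points. High end: (0.9×253.8 + 0.5×102.6)/356.4 = 78 points.

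8. *Sensitivity and specificity.* Illustration on all 1,200 women (804 HPV-positive, 396 HPV-negative), with 250 true positives and 12 false negatives under the rule (assumed). Sensitivity is 250/262 = 95.4% and specificity 384/938 = 40.9%. Adding 57 undiagnosed HPV-positive cases with 0 or 10 undiagnosed HPV-negative cases gives sensitivity 307/319 = 96.2% or 307/329 = 93.3%. Adding only 3.2 HPV-negative cases lowers specificity to 380.8/934.8 = 40.7%; adding only the 57 HPV-positive cases raises it to 384/881 = 43.6%. Neither measure has a fixed direction.

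**The case against.** The rule is openly stated, Table 1 shows the unbiopsied count in each group, no success criterion rests on Table 9, and the primary kappa does not use it. All of that stands and limits the seriousness. It does not test the rule, because Table 1 does not split the count by HPV result, and PPV and NPV depend on that split.

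A reader might infer that the error lies chiefly in Group 5. The documents do not support this. It is plausible for PPV at CIN2+ and CIN3+, but 89% of expected HPV-negatives are in Groups 1-4, and women who entered Group 5 on tissue already have a diagnosis.

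A reader might also infer that a Group 5 woman with histological CIN3 at entry and no new biopsy would be scored negative. That is the least natural reading, since the footnote concerns absence of a histological diagnosis and the standard is the most serious one. It remains open only because the window is undefined and Table 1 keeps past histology separate.

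A third tempting inference is that Relative accuracy is tilted towards the physician sample. The physician HPV result goes to the doctor while the self-collected result stays blinded until after the trial (Protocol, Study design and methods, F). Biopsy could therefore follow the physician result, but this is not established. Work-up may follow the abnormality found before entry, or precede an HPV result that needs two shipments and DNA extraction. If biopsy is unrelated to HPV result and the two samples are equally accurate, the comparison is unbiased.

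Finally, full bounds may be too wide to guide anyone. That may prove true, but the width would show how little the unverified part of the cohort tells us.

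**Conclusion.** The point holds as a cheap improvement. Followed as written, the footnote makes Table 9 report the minimum PPV and maximum NPV as the estimate. This rests on two conditions: the histology obtained is correct, and unverified women stay in the denominator.

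The size cannot be fixed from the documents, because they give neither the share without histology nor the disease rate among those women. Group 5 matters most for PPV at CIN2+ and CIN3+; NPV and CIN1+ depend largely on Groups 1-4. A tilt in Relative accuracy between equally accurate samples is conditional on biopsy following the physician result, and should not be presented as a finding. The primary kappa test and its required 1,049 cases are unaffected.

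**What to change.** 1. Report the share of women with histology by group, by physician HPV result and by self-collected HPV result.
2. Define the reference standard. State the histology window (the 90 days already used for smears in Table 3 is one option), that entry histology of untreated Group 4 and 5 women counts, and whether smear counts. Do not score a woman with a moderate or severe smear and no histology as a confirmed negative.
3. Beside the footnote result, show best-case and worst-case bounds for unverified women over all five groups together and by group. Bounds restricted to Groups 4 and 5 would leave out Groups 1-3, which hold 253.8/356.4 = 71% of expected HPV-negatives.
4. Optionally add a verification-weighted (Begg-Greenes type) sensitivity analysis. State its assumption that biopsied and unbiopsied women in the same stratum have the same disease rate. It is worse than the footnote when the rate in biopsied women is more than twice that in unbiopsied women. For example, with 70% biopsied, 60% of them diseased and 10% of the rest diseased, the truth is 0.7×60 + 0.3×10 = 45%, the footnote gives 42% and weighting gives 60%. Some strata will be sparse: Group 1 has about 11 expected HPV-positives. It should not replace the bounds.

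The cost is SAP wording and some extra programming on data already collected, with no new procedures. The downside is that the bounds may be wide, as step 7 of the working shows.
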